4. STUDY DESIGN

4.1. Overall Design

This study will be a randomised, double blind, placebo-controlled, two-period, crossover repeat dose study in adult subjects with asthma.

Following screening, subjects will provide AM and PM FeNO and PEF data from Day -7 of Treatment Period 1. The Day -7 AM FeNO readings will be used to confirm eligibility (FeNO >40ppb). On Day 1, pre-treatment (AM) FeNO, FEV₁ and PEF readings will be used as baseline for Treatment Period 1. Subjects will then receive FF/VI 100/25 or placebo once daily (AM) for 14 (\pm 2) days. All treatments will be taken at the same time of day (within \pm 2 hours of the treatment on Day 1).

FeNO will be measured by the subjects AM (pre-dose) and PM for 14 days during each treatment period. On Day 14, FEV₁ and FeNO will be recorded before the final dose of FF/VI or placebo.

FeNO (AM and PM) will be measured for 21 days after the end of treatment (up to Day 35 for each of the two treatment periods). This will be as an in-patient on Days 14 to 19. All FeNO (out-patient and in clinic) measurements will be obtained using the same FeNO meter for each subject.

FEV₁ will be recorded AM and PM (i.e. every 12 hours) as an in-patient on Days 14 to 19. Subjects will then be discharged before returning 2 days later (on Day 21) for a further measurement of FEV₁ (168 hours post-treatment). An FEV₁ measurement will also be performed on Day 35.

Up to 4 weeks after the final assessment is collected on Day 35 of Treatment Period 1, subjects will then be crossed over to the alternative treatment. Baseline FEV₁, PEF and FeNO values will be collected pre-treatment in the morning on Day 1: these will be the baseline values for Treatment Period 2. Subjects will then receive FF/VI 100/25 or placebo once daily (AM) for 14 (\pm 2) days. The second treatment period procedures will be identical to the first treatment period.

[figure not shown]
A single measurement of FeNO will be collected according to ATS/ERS guidelines at each time point, using a NIOX Vero device with electronic data capture. Appropriate dietary and/or lifestyle restrictions will be applied. The order of assessments collected in the clinic will be: FeNO, FEV₁, and then PEF. When the subjects are at home, FeNO will be collected before the PEF measurements. FEV₁ measurements taken within 6 hours of SABA use will not be analysed.

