4.2. Treatment Arms and Duration

Each subject will participate in two treatment periods of 14 (\pm 2 days). FF/VI 100/25 mcg will be received once daily (AM dosing) in one period and placebo (AM dosing) will be administered in the other period. At the end of each treatment period, there will be a monitoring period of 21 days. At the end of this monitoring period following Treatment Period 1, there may be a period of up to a further 4 weeks before the subjects start Treatment Period 2.

A schematic is shown below:

Total duration for each subject (from screening to follow-up) will be a minimum of 76 days, with a maximum of up to 21 weeks, depending on the screening period and the time period between Treatment Periods 1 and 2. The screening visit can be combined with the Day -7 visit if convenient. Likewise, if no gap is required between Treatment Period 1 and Treatment Period 2, the Day 35 visit for Treatment Period 1 can be combined with the Day 1 visit of Treatment Period 2.

A complete subject is one who has completed both treatment periods, all assessments up to Day 35 of both treatment periods, and all of the follow-up assessments.

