6. STUDY TREATMENT

6.1. Investigational Product

The term 'study treatment' is used throughout the protocol to describe any combination of products received by the subject as per the protocol design. Study treatment may therefore refer to the individual study treatments or the combination of those study treatments.

| | Study Treatment | |
|---|---|--|
| Product name: | FF/Vilanterol Inhalation Powder , 100/25 mcg per blister | Placebo To Match FF/Vilanterol Inhalation Powder |
| Formulation description: | First strip: FF blended with lactose, 100 mcg per blister Second strip: Vilanterol blended with lactose and magnesium stearate ¹ , 25 mcg per blister ² | First strip: lactose Second strip: lactose and magnesium stearate ¹ |
| Dosage form: | Dry Powder Inhaler | Dry Powder Inhaler |
| Unit dose strength(s)/Dose level(s): | FF/Vilanterol 100/25 mcg ² | N/A |
| Route of Administration/ Duration: | Inhaled/ Taken once a day for 14 ± 2 days | Inhaled/Taken once a day for 14 ± 2 days |
| Dosing instructions: | 1 inhalation | 1 inhalation |
| Physical description: | Dry powder Inhaler | |
| Manufacturer/ source of procurement: | GSK | GSK |

1. Magnesium stearate 1% w/w of total drug product

2. 40 mcg of Vilanterol trifenate (triphenylacetate salt) is equivalent to 25 mcg of Vilanterol (free base).

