6.6. Compliance with Study Treatment Administration

When subjects are dosed at the site (on Day 1 and Day 14 of each treatment period), they will receive study treatment directly from the investigator or designee, under medical supervision. The date and time of each dose administered in the clinic will be recorded in the source documents. The dose of study treatment and study subject identification will be confirmed at the time of dosing by a member of the study site staff other than the person administering the study treatment.

When subjects self-administer study treatment at home (on Days 2 to 13 of each treatment period), dosing details will be completed by the subjects in individual paper diaries, and then later transcribed by the site into the CRF. Dosing compliance will be assessed through querying the subject during the subsequent site visits and this will be documented in the source documents and CRF. A dosing record for each subject must be maintained and reconciled with study treatment and compliance records.

Subject compliance with study treatment administered at home will be reinforced by the site using various methods including the use of daily text reminders and weekly telephone contact. More details will be given in the SRM.

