7.1. Time and Events Table

| Procedure | Screening (up to 42 days prior to Day 1) | Study Day (each treatment period) | | | | | | Follow-up (Days 35- 42) ¹³ | Notes |
|---|---|---|----------------|---------------|----------------|-----------|-----------|---|--|
| | | Day -7 (start of run-in) ¹ | Day 1 | Days 2- 13 | Days 14-19 | Day 21 | Day 35 | | |
| Out-patient visit to the unit | X | X | X | | | X | X | X | ¹ Day -7 is the start of the one week run-in period and therefore this visit and the assessments on this day only apply to Treatment Period 1 |
| Admission to the unit | | | | | X | | | | |
| Informed consent | X | | | | | | | | |
| Inhaler, PEF meter and FeNO device practice | X | | | | | | | | |
| Inclusion and exclusion criteria/eligibility review | X | X | X ² | | | | | | ² Treatment Period 1 only |
| Demography | X | | | | | | | | |
| Full physical exam including height and weight | X | | | | | | | | |
| Medical history (includes substance usage [and family history of premature CV disease]) | X | | | | | | | | Substances: [Drugs, Alcohol, tobacco and caffeine] |
| Past and current medical conditions [including cardiovascular medical history] | X | | | | | | | | |
| Urine pregnancy test (WCBP) | X | | X ³ | | | X | | X | ³ Collected pre-dose |
| Vital signs | X | | | | | | | | |
| Set up PEF and FeNO monitoring | | X | | | | | | | |
| Study Treatment | | | X ⁴ | | X ⁵ | | | | ⁴ Dosing every morning; dosing in the unit on Days 1 and 14 and at home on Days 2-13 ⁵ Dosing on the morning of Day 14 only |

| Procedure | Screening (up to 42 days prior to Day 1) | Study Day (each treatment period) | | | | | | Follow-up (Days 35- 42) ¹³ | Notes |
|---|---|---|----------------|---------------|----------------|-----------------|-----------------|---|---|
| | | Day -7 (start of run-in) ¹ | Day 1 | Days 2- 13 | Days 14-19 | Day 21 | Day 35 | | |
| Exploratory biomarker sampling ⁶ | | | X | | X | X | X | | ⁶ These measurements are taken at baseline (Day 1 pre-dose), at the end of treatment (Day 15), on Day 21 and on Day 35. |
| FEV ₁ readings ⁷ | X | | X ⁸ | | X ⁹ | X ¹⁰ | X ¹⁰ | | ⁷ Measured in the unit only ⁸ Taken pre-dose ⁹ Collected AM (pre-dose on Day 14) and PM ¹⁰ Collected AM only |
| FeNO assessment ¹¹ | X | ←=====→ | | | | | | | ¹¹ Start of collection 7 days before Day 1 (Day -7), then collected every day AM and PM through to Day 35 of each treatment period. |

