2.3. Study Design

Overview of Study Design and Key Features	

The diagram illustrates the study design timeline. It starts with a 'Run in (SABA only)' phase. Treatment Period 1 begins on Day 1 with FF/VI 100/25 for 14 days, followed by a 21-day Washout period. Treatment Period 2 is identical to Period 1, separated by a crossover period. Clinical units and measurements are indicated by 'X' marks and arrows.
	
Design Features	This study is a randomized, double-blind, placebo-controlled, two-period, crossover repeat dose study to characterise the exhaled nitric oxide time profile as a biomarker of airway inflammation in adult asthmatics.
Dosing	Each subject will participate in two treatment periods of 14 (+/- 2 days). FF/VI 100/25 mcg will be received once daily (AM dosing) in one period and placebo (AM dosing) will be administered in the other period. At the end of each treatment period, there will be a monitoring period of 21 days. Following the 21 day monitoring period following treatment period 1, there may be a period of up to a further 4 weeks before the subjects start treatment period 2. Total duration for each subject (from screening to follow-up) will be a minimum of 11 weeks, with a maximum of up to 21 weeks, depending on the screening period and the time period between Treatment Periods 1 and 2

Overview of Study Design and Key Features	
Treatment Assignment	Subjects will be randomized to one of two sequences AB or BA. Where, A=Placebo and B=FF/VI 100/25mcg. Subjects will be administered the first treatment in the sequence in the first period and the second treatment in the sequence in the second period.

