11.5.3. Reporting Process & Standards

Reporting Process	
Software	

 The currently supported versions of SAS software will be used. 	
Reporting Area	
HARP Server	: UK1SALX00175-HARP PROD-UK
HARP Area	: \ARPROD\ GW685698+GW642444\mid201499\Final
QC Spreadsheet	: \ARWORK\ GW685698+GW642444\mid201499\Final\Documents
Analysis Datasets	

 Analysis datasets will be created according to Legacy GSK A&R dataset standards 	
Generation of RTF Files	

 RTF files will be generated for summary displays. 	

Reporting Standards	
General	

 The current GSK Integrated Data Standards Library (IDSL) will be applied for reporting, unless otherwise stated: 
 4.03 to 4.23: General Principles 5.01 to 5.08: Principles Related to Data Listings 6.01 to 6.11: Principles Related to Summary Tables 7.01 to 7.13: Principles Related to Graphics 	
Formats	

 All data will be reported according to the actual treatment the subject received unless otherwise stated. GSK IDSL Statistical Principles (5.03 & 6.06.3) for decimal places (DP's) will be adopted for reporting of data based on the raw data collected. Numeric data will be reported at the precision collected on the eCRF. The reported precision from non eCRF sources will follow the IDSL statistical principles but may be adjusted to a clinically interpretable number of DP's. 	

Planned and Actual Time	

 Reporting for tables, figures and formal statistical analyses : 
 Planned time relative to dosing will be used in figures, summaries, statistical analyses and calculation of any derived parameters, unless otherwise stated. The impact of any major deviation from the planned assessment times and/or scheduled visit days on the analyses and interpretation of the results will be assessed as appropriate. Reporting for Data Listings: 
 Planned and actual time relative to study drug dosing will be shown in listings (Refer to IDSL Statistical Principle 5.05.1). Unscheduled or unplanned readings will be presented within the subject’s listings. Visits outside the protocol defined time-windows (i.e. recorded as protocol deviations) will be included in listings but omitted from figures, summaries and statistical analyses. 	
Unscheduled Visits	

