11.6. Appendix 6: Derived and Transformed Data

11.6.1. General

Multiple Measurements at One Time Point

- Mean of the measurements will be calculated and used in any derivation of summary statistics but if listed, all data will be presented.
- If there are two values within a time window the value closest to the target day for that window will be used. If values are the same distance from the target then the mean will be taken.

Study Day

- Calculated as the number of days from randomisation date :
 - Ref Date = Missing → Study Day = Missing
 - Ref Date < Treatment start Date → Study Day = Ref Date – Treatment start Date
 - Ref Date ≥ Treatment start Date → Study Day = Ref Date – (Treatment start Date) + 1

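### Is the primary FeNO time axis undefined because the SAP does not tie post-cessation Day to the actual last dose, or assign the PM reading on a combined Day 35?

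*SAP*

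**What the plan says.** - **Course length.** Protocol 6.1: "Taken once a day for 14 ± 2 days". SAP 2.3 repeats the tolerance.
- **Time scale.** SAP 11.5.3: "Planned time relative to dosing will be used in figures, summaries, statistical analyses and calculation of any derived parameters, unless otherwise stated".
- **Day formula.** SAP 11.6.1 introduces Study Day with "Calculated as the number of days from randomisation date", but the formula beneath counts from the treatment start date. It is the only day derivation in the SAP.
- **Last dose.** Protocol 4.1 says that on Day 14 FEV₁ and FeNO "will be recorded before the final dose of FF/VI or placebo". It describes FeNO follow-up as 21 days from the end of treatment, to Day 35, and puts Day 21 at 168 hours. The Time and Events Table (Protocol 7.1, SAP Appendix 3) has unit dosing on Days 1 and 14 and home dosing on Days 2 to 13.
- **Combined visit.** Protocol 4.2: if no gap is needed, "the Day 35 visit for Treatment Period 1 can be combined with the Day 1 visit of Treatment Period 2". FeNO is "then collected every day AM and PM through to Day 35 of each treatment period" (Protocol 7.1).
- **Treatment attribution.** Protocol 9.3.1 and SAP 11.5.3 analyse and report data by the treatment actually received.

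**The concern.** The study exists to time the loss of anti-inflammatory effect after the last dose, so the time axis is the substance of the primary result. If Day were counted from treatment start, a 16-day course would put four readings taken at or before the last dose (Day 14 PM to Day 16 AM) into the post-cessation model. A 12-day course would put four off-drug readings into the on-treatment analysis. Day 21 would no longer be 168 hours for either subject. The SAP's rules on out-of-window visits and major timing deviations need not help, because a 12- or 16-day course is within protocol.

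On a combined Day 35, dosing is in the morning, so the PM reading follows the first dose of the next period. For a placebo-first subject, a reading nominally in the placebo period would have been taken on FF/VI. The SAP's rule for two values in one window does not cover one value that fits two periods.

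**Working it through.** **1. Which Day 14 do the plan's own figures imply?**

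Hours since last dose = (visit day − last-dose day) × 24. With the last dose on Day 14, (21 − 14) × 24 = 168 h, the protocol's figure. Counting Day from treatment start gives:

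| Last dose on | Day 15 AM | Day 21 AM | Day 35 AM |
|---|---|---|---|
| Day 12 | 72 h | 216 h | 23 days |
| Day 14 | 24 h | 168 h | 21 days |
| Day 16 | −24 h | 120 h | 19 days |

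Only the middle row agrees with the 168 hours, the 21 days of follow-up and the 21-day minimum washout in Protocol 4.4. So the schedule treats Day 14 as the last-dose visit. The analysis documents fit this. SAP 11.5.3 uses planned time, whereas Study Day in 11.6.1 is built from actual dates, and nothing says the model's Day factor is that variable. The shell for the primary table (SAP Appendix 11, PD_T1) has columns for visit and planned timepoint. SAP 7.1.2 defines the endpoint as after cessation, so a reading before the last dose is outside it.

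**2. Size if Day were nevertheless counted from treatment start.**

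Assumptions not in the documents: the FF/VI to placebo ratio is 0.50 at the last dose, and the log ratio decays with half-life h. Then log ratio(t) = ln(0.5) × 2^(−t/h), with t floored at 0 and means taken on the log scale. At nominal 48 h:

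| h (days) | True ratio | Last doses evenly over Days 12–16 | Evenly over Days 14–16 |
|---|---|---|---|
| 2 | 0.707 | 0.677 (−4.2%) | 0.601 (−15.1%) |
| 3 | 0.646 | 0.631 (−2.3%) | 0.571 (−11.6%) |
| 5 | 0.591 | 0.585 (−1.0%) | 0.545 (−7.9%) |

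With h = 3 and 10%, 25% or 50% of subjects on 16 days and the rest on 14, the ratio is 0.630, 0.606 or 0.568. The time to reach 0.80 moves from 4.9 days to 5.1 (symmetric) or 6.0 (one-sided).

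Planned precision for comparison (Protocol 9.2.1, CVw 21.6%, n = 24): exp(2.074 × √ln(1 + 0.216²) × √(2/24)) − 1 = 13.6%, against the stated figure of about 14%.

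**3. The combined day.**

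The protocol's 76-day minimum is 7 + 34 + 35, which needs the shared day; separate days give 7 + 35 + 35 = 77. The SAP's version, "Total duration for each subject (from screening to follow-up) will be a minimum of 11 weeks", is 77 days exactly, or 76/7 = 10.9 weeks rounded. No analysis uses it.

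Post-cessation timepoints from Day 14 PM to Day 35 PM number 1 + 21 × 2 = 43, and only the last is in question. The AM reading on that day precedes the Period 2 dose, so it can be both Day 35 AM and the Period 2 baseline. In the FF/VI-first sequence the PM reading follows a placebo dose, so only placebo-first subjects matter. If a first dose lowers FeNO by d at 12 h and a fraction f of subjects combine visits (both assumed), with half placebo-first, the ratio at that timepoint is inflated by (1 − d)^(−f/2):

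- d = 5%, f = 25%: 1.006
- d = 10%, f = 50%: 1.027
- d = 20%, f = 100%: 1.118

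**The case for a change.** The strongest opposing case is that the SAP never states the sensible reading, and two programmers could build different primary datasets without breaching it. The only written day formula counts from treatment start. Home FeNO readings come off a device by date and must be mapped to a Day by some rule. Even with Day 14 fixed as the last-dose visit, home dosing labels stop at Day 13, so a 16-day course leaves four on-treatment readings (two days, AM and PM) without a planned label. The cure would be a few lines of text, using dose times and FeNO records that are already collected.

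The silence is real, and so is the home-label gap. But those four readings bear only on the secondary on-treatment analysis, and SAP 11.5.3 already sends unplanned readings to the listings. Mapping later home readings from the last-dose visit follows from the protocol's 21 days of follow-up after treatment ends. The 19-day washout, which would conflict with the 21-day minimum and need reconciling, arises only if Day 35 is counted from treatment start. The mismatch in 11.6.1 between the randomisation date and the treatment start date is a clerical slip.

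On the combined day, the actual-treatment rule answers the worry about placebo: a reading taken after an FF/VI dose is not placebo data. On planned time relative to dosing it is the 12-hour reading of Period 2 Day 1. The 1.118 factor also needs every subject to combine visits and a 20% fall within 12 hours of a first dose, whereas Protocol 4.4 puts the onset of the ICS effect within a few days.

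**Conclusion.** No change is called for. The SAP leaves a labelling rule unwritten, and the protocol's schedule, the endpoint definition, the primary table shell and the actual-treatment rule all point to one answer. Post-cessation Day runs from the last-dose visit, and the PM reading on a combined day belongs to Period 2. On that reading the in-patient part of the primary curve is unaffected, and what remains is a few unlabelled home readings in a secondary analysis.

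No bias has been demonstrated. The 8% to 15% errors need Day counted from treatment start, which no passage requires for the model, together with two-thirds of subjects running over and none under. The stated tolerance is symmetric, and the symmetric case gives 1% to 4%, well inside the 13.6% half-width. All these sizes rest on an assumed 50% suppression and a half-life of 2 to 5 days, and the documents do not give the share of courses that differ from 14 days. If many courses ran long and the programming did count from treatment start, the error would matter (about 12% with half the subjects on 16 days and h = 3). That would mean departing from the schedule's own Day 14 and 168-hour figures.

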11.6. Appendix 6: Derived and Transformed Data

11.6.1. General

Multiple Measurements at One Time Point

- Mean of the measurements will be calculated and used in any derivation of summary statistics but if listed, all data will be presented.
- If there are two values within a time window the value closest to the target day for that window will be used. If values are the same distance from the target then the mean will be taken.

Study Day

- Calculated as the number of days from randomisation date :
 - Ref Date = Missing → Study Day = Missing
 - Ref Date < Treatment start Date → Study Day = Ref Date – Treatment start Date
 - Ref Date ≥ Treatment start Date → Study Day = Ref Date – (Treatment start Date) + 1

11.6.2. Study Population

Demographics

Age

- GSK standard IDSL algorithms will be used for calculating age where birth date will be imputed as follows:
 - Any subject with a missing day will have this imputed as day '15'.
 - Any subject with a missing date and month will have this imputed as '30th June'.
- Birth date will be presented in listings as 'YYYY'.

Body Mass Index (BMI)

- Calculated as **Weight (kg) / [Height (m)²]**

Extent of Exposure

- Number of days of exposure to study drug will be calculated based on the formula:
Duration of Exposure in Days = (Treatment Stop Date – Treatment Start Date) + 1
- Subjects who were randomized but did not report a treatment start date will be categorised as having zero days of exposure.
- The cumulative dose will be based on the formula:
Cumulative Dose = Sum of (Number of Days x Total Daily Dose)

11.6.3. Pharmacodynamic

FeNO
Period level baseline

 • The Period-Specific Baseline value is the pre-dose assessment collected on day 1 of each treatment period • Period level baseline is defined as the difference between the baseline and subject level baseline for each period and each subject.
Subject level baseline

 • Subject level baseline is defined as the mean of baseline across periods for each subject.

Laboratory Parameters

 • If a laboratory value which is expected to have a numeric value for summary purposes, has a non-detectable level reported in the database, where the numeric value is missing, but typically a character value starting with '<x' or '>x' (or indicated as less than x or greater than x in the comment field) is present, the number of significant digits in the observed values will be used to determine how much to add or subtract in order to impute the corresponding numeric value. 
 ○ Example 1: 2 Significant Digits = '< x ' becomes $x - 0.01$ ○ Example 2: 1 Significant Digit = '> x' becomes $x + 0.1$ ○ Example 3: 0 Significant Digits = '< x' becomes $x - 1$

11.7. Appendix 7: Premature Withdrawals & Handling of Missing Data

11.7.1. Premature Withdrawals

Element	Reporting Detail
General	
 • Subject study completion (i.e. as specified in the protocol) was defined as subject is one who has completed both treatment periods, all assessments up to Day 35 of both treatment periods, and all of the follow-up assessments. The end of the study is defined as the last subject's last visit. • Withdrawn subjects were not replaced in the study. • All available data from subjects who were withdrawn from the study will be listed and all available planned data will be included in summary tables and figures, unless otherwise specified.

